1. ABBREVIATIONS AND DEFINITIONS

Please add study specific abbreviations and definitions.

	e.g.:					
--	-------	--	--	--	--	--

AE	Adverse Event
A(D)R	Adverse (Drug) Reaction
С	Control
CANTAB	Cambridge Neuropsychological Test Automated Battery
CRB	Cerebrolysin
CRF	Case Report Form
CRO	Contract Research Organisation
СТ	Computed tomography
DLPFC	Dorso-lateral pre-frontal cortex
ET	Eye tracking
FSNN	Foundation for the Study of Neuroprotection and Neuroplasticity
GCP	Good Clinical Practice
GCS	Glasgow Coma Scale
GCS Н	Glasgow Coma Scale Hour
	-
н	Hour
H HA	Hour Alternative Hypothesis
H HA HAM-A	Hour Alternative Hypothesis Hamilton Anxiety Rating Scale
H HA HAM-A HAM-D	Hour Alternative Hypothesis Hamilton Anxiety Rating Scale Hamilton Rating Scale for Depression
H HA HAM-A HAM-D H0	Hour Alternative Hypothesis Hamilton Anxiety Rating Scale Hamilton Rating Scale for Depression Null-hypothesis
H HA HAM-A HAM-D H0 Hz	Hour Alternative Hypothesis Hamilton Anxiety Rating Scale Hamilton Rating Scale for Depression Null-hypothesis Hertz
H HA HAM-A HAM-D H0 Hz ICH	Hour Alternative Hypothesis Hamilton Anxiety Rating Scale Hamilton Rating Scale for Depression Null-hypothesis Hertz International Conference for Harmonization
H HA HAM-A HAM-D H0 Hz ICH IEC	Hour Alternative Hypothesis Hamilton Anxiety Rating Scale Hamilton Rating Scale for Depression Null-hypothesis Hertz International Conference for Harmonization Independent Ethics Committee

STUDY ID: CAPTAIN - rTMS

Page 11 of 58

IUD	Intrauterine device
ITT	Intention-to-treat
IV	Intra-venous
LOCF	Last Observation Carried Forward
LPFC	Last Percentile Carried Forward
MCAR	Missing completely at random
mL	Milli Liter
MoCA	Montreal Cognitive Assessment Scale
MNAR	Missing not at random
MRI	Magnetic resonance imaging
MTT	Multi-tasking test
MW	Mann-Whitney
NA	Not Applicable
OTS	One Touch Stocking of Cambridge
PLC	Placebo
PP	Per protocol
PSI	Processing Speed Index
qEEG	Qantitative electroencephalography
rTMS	Repetitive transcranial magnetic stimulation
RT	Reaction Time
SAP	Statistical analyses plan
SAE	Serious Adverse Event
SAP	Statistical Analyses Plan
SAR	Serious Adverse Reaction
SESAR	Suspected Expected Serious Adverse Reaction
SOP	Standard Operating Procedure
SmPC	Summary of Product Characteristics
SUSAR	Suspected Unexpected Serious Adverse Reaction
т	Test Treatment

Date: 040418

Page 12 of 58

ТВІ	Traumatic Brain Injury
WAIS	Wechsler Adult Intelligence Scale
WHO-UMC	World Health Organization-Uppsala Monitoring Center

Date: 040418

2. PROTOCOL SUMMARY / SYNOPSIS

Title	
Investigational Medicinal Product	R-TMS + Cerebrolysin Solution for Injection
Number of Sites & Countries	1 site, 1 country
Phase	II
Indication	Traumatic Brain Injury
Study Design	monocentric, randomized, double-blind, phase II study
Study Duration	Study start: 04/2018 Study end: 12/2020
Sample Size	 Treatment Group CRB + rTMS: N=30 Treatment Group CRB + sham rTMS: N=30 Treatment Group placebo + sham rTMS: N=30
Primary Objective	To assess the efficacy of the combined rTMS and Cerebrolysin treatment versus CRB alone, upon a battery of neurocognitive outcomes at 3 and 6 months post TBI
Secondary Objectives	To assess the single efficacy criteria at three and six months post TBI To test ET and qEEG parameters as biomarkers of cognitive dysfunction To assess the safety of rTMS administrated starting with one month after TBI

Primary Variables	To check assay sensitivity for the primary objective (rTMS + CRB versus CRB alone) by comparing CRB alone versus PLC. Processing Speed Index, Stroop Color-Word Test, Trail Making Test, Digit Span, Montreal Cognitive Assessment, One Touch Stockings of Cambridge (CANTAB), Reaction Time (CANTAB), Multitasking Test (CANTAB), Hamilton Rating Scale for Depression, Hamilton Anxiety Rating	
Secondary Variables	Scale) Eye tracking parameters Quantitative EEG parameters	
Inclusion Criteria	 rTMS adverse events Traumatic brain injury onset 30 days prior to screening CT/MRI – focal and/or diffuse lesions 	
	 Age: 18-70 years, inclusive Pre-Trauma Karnofsky Index 100 Patient is willing and able to comply with the protocol requirements for the duration of the study 	
Exclusion Criteria	 Metal implant in the head or within the stimulation area Medical implanted devices (cardiac pacemaker, cochlea implant or medication pumps) History of intracranial interventions as well as ischemic or hemorrhagic stroke Evidence of pre-existing major health problems (e.g., cancer, hematological, renal, hepatic, or coronary disease, psychiatric disorder, diabetes, myocardial infarction or other known heart diseases, disabling or musculoskeletal problems as rheumatoid arthritis, 	

	epilepsy, evidence of degenerative or inflammatory
	diseases affecting nervous system [e.g., Alzheimer, Parkinson]). Patients with well controlled diabetes and
	hypertension can be included if there is no evidence of
	secondary damage to major organs.
	 Any neurological or non-neurological condition
	independent from TBI that might influence the
	functional outcome or other efficacy outcome
	measures.
	• Injury of writing hand influencing cognitive or other
	outcome measures, in the investigator's judgment.
	Clear clinical signs of intoxication influencing the
	evaluation, in the investigator's judgment.
	• Major drug dependency including alcohol, in the
	investigator's judgment.
	Chronic treatment with steroids, Ca2+-channel
	blockers or major anticoagulants (e.g., warfarin and
	other coumarin derivates), monoamine oxidase
	inhibitors, antipsychotic drugs or nootropic molecules.
	Patient with penetrating brain injury.
	Females who are pregnant or lactating.
	• Females who are of child bearing potential and not
	taking adequate contraceptive precautions are
	excluded from the trial. Females of child bearing
	potential taking acceptable contraceptive precautions
	can be included. A highly effective method of birth
	control and one which is acceptable for this study, is
	defined as those which result in a low failure rate (i.e.
	less than 1% per year) when used consistently and
	correctly such as implants, injectables, combined oral
	contraceptives, some IUDs, sexual abstinence or
	vasectomised partner.
Visit Schedule	Screening and Baseline – Study day 0 (within 30 days
	after TBI onset)

 Neurological and physical exam Hematology and blood chemistry Demographic data Medical history Evaluation Scales: Processing Speed Index, Stroop Color-Word Test, Trail Making Test, Digit Span, Montreal Cognitive Assessment, One Touch Stockings of Cambridge (CANTAB), Reaction Time (CANTAB), Multitasking Test (CANTAB), Hamilton Rating Scale for Depression, Hamilton Anxiety Rating Scale ET qEEG
 Treatment cycles Study day 31-40 Study day 61-70 Study Day 91-100 Visit 1 – Efficacy Evaluation (Study Day 101)
 Neurological and general exam Evaluation Scales: Processing Speed Index, Stroop Color-Word Test, Trail Making Test, Digit Span, Montreal Cognitive Assessment, One Touch Stockings of Cambridge (CANTAB), Reaction Time (CANTAB), Multitasking Test (CANTAB), Hamilton Rating Scale for Depression, Hamilton Anxiety Rating Scale ET qEEG Visit 2 – Efficacy Evaluation (Study Day 180)

	Neurological and general exam
	 Evaluation Scales: Processing Speed Index, Stroop Color-Word Test, Trail Making Test, Digit Span, Montreal Cognitive Assessment, One Touch Stockings of Cambridge (CANTAB), Reaction Time (CANTAB), Multitasking Test (CANTAB), Hamilton Rating Scale for Depression, Hamilton Anxiety Rating Scale ET qEEG
Investigational Product Characteristics	 IV Cerebrolysin (CRB), 30 ml diluted in 0.9% saline solution up to 250 ml, daily during 10 consecutive working days; three treatment cycles during study days 31-40, 61-70 and 91-100) The rTMS treatment will be performed daily during 10 consecutive working days; three treatment cycles during study days 31-40, 61-70 and 91-100) The device MagPro X100 (MagVenture, Denmark) will be used for repetitive stimulation with a figure-8 coil (MCF-B65). The coil will be hold tangential to the scalp with the handle pointing upwards. For localizing the left dorsolateral prefrontal cortex (DLPFC) stimulation, we will use the 10-20 EEG system by placing the coil at F3. The stimulation parameters for DLPFC will be set up at 10 Hz and 1,200 stimuli/day, with an intensity of 120% of resting motor threshold. The resting motor threshold is determined at the beginning of the first treatment session and is defined as the minimal intensity at which at least five of 10 motor evoked potentials are 50 µV in amplitude in the pollicis abductor brevis.

Date: 040418

STUDY ID: CAPTAIN - rTMS

Page 18 of 58

Reference Product	Standard TBI treatment
-------------------	------------------------

3. INTRODUCTION

3.1. Background information

After an acute brain lesion, there is always an endogenous continuous brain defense response consisting of two main sequences: an immediate one that aims to reduce brain damage, known as neuroprotection, and a later one that aims to repair the brain damage, known as neurorecovery, which is based on neurotrophicity, neuroplasticity and neuro-genesis.

Neurotrophic factors are the most important endogenous molecules involved in brain protection and recovery. They are modulating molecules with immediate pleiotropic neuroprotective activity and long-term multimodal effects. Due to this unique therapeutic effect, the principle of treatment with neurotrophic factors is based on, in addition to acute administration, repetitive periods of treatment. This principle is applied to stimulate long-term endogenous capacity for neurorecovery that is induced by neurotrophicity, neuroplasticity and neurogenesis.

Cerebrolysin has a neurotrophic factor-like activity based on the four important endogenous neurobiological processes: neurotrophicity, neuroprotection, neuroplasticity and neurogenesis. Additionally, this activity may have similar effects as the real sequence of endogenous post-lesional regulation.

Transcranial magnetic stimulation (TMS) operates on Faraday's principle of electromagnetic induction.

There are several studies regarding a beneficial role of repetitive TMS (rTMS) in neurorehabilitation, including in TBI patients such as: motor recovery including spasticity, depression treatment, and speech rehabilitation (Fitzgerald, 2011; Bonni, 2013; Castel-Lacanal, 2013, Krewer, 2014).

According with the paradigm that rTMS effects are based on the induction of potential actions, most of the studies regarding the effect of rTMS on cognition are based on the idea that stimulating with different frequencies on a certain area, will activate/deactivate specific regions or even networks and so will enhance/inhibit specific functions. However, the experimental studies, showed that rTMS influence also the molecular and cellular level, influence that can be independent from the induction of action potentials. One of the key targets by which rTMS improves cognitive function appears to be BDNF, magnetic stimulation having a stimulating effect on its genetic expression.

Even that rTMS has extensively been tested in patients with Alzheimer's disease (Liao, 2015), in TBI there is a little date about rTMS in cognitive rehabilitation.

A recently published article described the effects of rTMS in various post-concussive symptoms, including cognitive dysfunction. There were administrated 20 sessions of RTMS (20 x 5-sec trains; 10-Hz at 110% threshold), with clinical and functional magnetic resonance imaging (fMRI) assessments before and after intervention, and clinical assessment at 3-month follow-up, in 15 patients with mild TBI. The results showed cognitive improvement and a decrease of post-concussive symptoms (Koski, 2014). The use of high frequency stimulation on DLPFC is concordant with data existing in literature in TBI, dementia, stroke and depression (Miniussi, 2011; Koski, 2014, Nadeau, 2014). There is a single case presented in literature with rTMS treatment for depression in TBI which represent a common complication in this pathology and is independently associated with decreased cognitive functions (Fitzgerald, 2011).

The main area of concern regarding the use of TMS in stroke or TBI patients has been the triggering of kindling activity, which can induce seizures Seizure induction, however, has rarely been reported following rTMS, and animal studies have shown that there is no clear evidence that rTMS leads to increased seizure susceptibility (Miniussi and Rossini, 2011).

3.2. Study Rationale

Cognitive treatment with rTMS was tested in Alzheimer's diseases and the combination between rTMS combined with cognitive treatment seems to have a beneficial effect upon cognition (Bentwich, 2011). Regarding rTMS as an add-on to pharmacological treatment in cognitive rehabilitation, there are too few data to establish its efficacy. (Haffen, 2012). There are several studies on rTMS as add-on treatment in depression, with good results when the magnetic stimulation was performed with high frequencies (Mogg, 2008; Chen, 2013). In TBI, this study is the first one in order to test the efficacy of the combining treatment rTMS + pharmacological intervention (CRB) in cognitive rehabilitation.

Date: 040418

4. STUDY OBJECTIVES

This study shall assess the efficacy of the combining treatment rTMS + pharmacological intervention (CRB) in cognitive rehabilitation of patients with traumatic brain injuries.

4.1. Primary Objective

It is the primary objective of this clinical study to assess the efficacy of the combining rTMS and Cerebrolysin treatment versus CRB alone, upon a battery of co-primary neurocognitive outcomes at 3 and 6 months post TBI.

4.1.1. Primary Variables

The scores and/score changes from baselines at 3 and 6 months post TBI of the following clinical scales: Processing Speed Index, Stroop Color-Word Test, Trail Making Test, Digit Span, Montreal Cognitive Assessment, One Touch Stockings of Cambridge (CANTAB), Reaction Time (CANTAB), Multitasking Test (CANTAB), Hamilton Rating Scale for Depression, Hamilton Anxiety Rating Scale

4.2. Secondary Objectives

- To assess the single efficacy criteria at 3 and 6 months post TBI.
- To test ET and qEEG parameters as biomarkers of cognitive dysfunction.
- To assess the safety of rTMS administrated starting with one month after TBI.
- To check assay sensitivity for the primary objective (rTMS + CRB versus CRB alone) by comparing CRB alone versus PLC.

Date: 040418

STUDY ID: CAPTAIN - rTMS

4.2.1. Secondary Variables

- Eye Tracking (ET) parameters
- Quantitative EEG (qEEG) parameters
- Safety Parameters (laboratory values, adverse events)

5. STUDY DESIGN

Monocentric, randomized, double-blind, phase II study

6. SELECTION AND WITHDRAWAL OF PATIENTS

6.1. Patient Inclusion Criteria

- Traumatic brain injury onset 30 days prior to screening
- CT/MRI– focal and/or diffuse lesions
- Age: 18-70 years, inclusive
- Pre-Trauma Karnofsky Index 100
- Patient is willing and able to comply with the protocol requirements for the duration of the study

6.2. Patient Exclusion Criteria

- Metal implant in the head or within the stimulation area
- Medical implanted devices (cardiac pacemaker, cochlea implant or medication pumps)
 - History of intracranial interventions as well as ischemic or hemorrhagic stroke
 - Evidence of pre-existing major health problems (e.g., cancer, hematological, renal, hepatic, or coronary disease, psychiatric disorder, diabetes, myocardial infarction or other known heart diseases, disabling or musculoskeletal problems as rheumatoid arthritis, epilepsy, evidence of degenerative or inflammatory diseases affecting nervous system [e.g., Alzheimer, Parkinson]). Patients with well controlled diabetes

and hypertension can be included if there is no evidence of secondary damage to major organs.

- Any neurological or non-neurological condition independent from TBI that might influence the functional outcome or other efficacy outcome measures.
- Injury of writing hand influencing cognitive or other outcome measures, in the investigator's judgment.
- Clear clinical signs of intoxication influencing the evaluation, in the investigator's judgment.

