13.13.3. ITT Population (Full Analysis Set)

ITT population is defined as all patients who have no "severe" violation of entry criteria, had at least one dose of medication and at least one post-baseline observation of at least one primary efficacy criterion ("modified" ITT). This way ITT is defined in the sense of the "full analysis set" according to ICH E9 § 5.2. ("Analysis Sets") . ITT population will be used for all efficacy analyses.

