13.2. Demographic and Other Baseline Characteristics

Patients' demographics will be obtained at Screening (study day 30), alongside medical history, neurological and physical examinations and hematology and blood chemistry will be obtained.

Females who are pregnant or lactating will be excluded from the study. However, females of child bearing potential taking acceptable contraceptive precautions can be included. A highly effective method of birth control and one which is acceptable for this study, is defined as those which result in a low failure rate (i.e. less than 1% per year) when used consistently and correctly such as implants, injectables, combined oral contraceptives, some IUDs, sexual abstinence or vasectomised partner.

Some concomitant medication will exclude the patient from the study: steroids, Ca2+-channel blockers or major anticoagulants (e.g., warfarin and other coumarin derivates), monoamine oxidase inhibitors, antipsychotic drugs or nootropic molecules. All other concomitant medications and therapies will be recorded in the CRF.

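### Section 6.2 carries only seven of the synopsis's 12 exclusions, and neither document says which list decides eligibility or entry-criteria violations

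*Protocol*

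**What the plan says.** The exclusion list in the protocol synopsis (section 2) opens with "Metal implant in the head or within the stimulation area" and runs to 12 items. Among its last five are "Major drug dependency including alcohol", "Patient with penetrating brain injury" and "Females who are pregnant or lactating". The other two cover chronic treatment with six named drug classes and women of child-bearing potential without adequate contraception.

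Protocol section 6.2, the section headed as the exclusion criteria, gives the first seven items in the same order. Its last item is "Clear clinical signs of intoxication influencing the evaluation, in the investigator's judgment", and section 6.3 follows directly.

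Two other places bear on eligibility. Protocol section 8 disallows three drug classes as concomitant medication. SAP section 13.2 states "Females who are pregnant or lactating will be excluded from the study", allows women of child-bearing potential who use acceptable contraception, and names all six drug classes as excluding a patient.

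Protocol section 6.4 gives a random number to patients who meet the inclusion and exclusion criteria, without naming a list. Protocol section 13.13.3, repeated in SAP section 10, restricts the ITT population to patients with no severe "violation of entry criteria, had at least one dose of medication" and at least one post-baseline observation of a primary criterion.

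**The concern.** A single-site trial should have one set of entry rules. Here there are four partly overlapping statements of them, and the section a site would naturally consult for exclusions is the shortest version of the list.

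Two things are at stake. The first is participant safety: nothing written in 6.2 excludes a pregnant or lactating woman, although the synopsis and the SAP both do. The second is the analysis population: the ITT set, on which the confirmatory analysis is run, drops patients for severe violations of entry criteria. Whether a patient violated a criterion at all can depend on which list the blind review uses.

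**Working it through.** No power or error-rate calculation applies. The check matches the lists item by item.

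| Synopsis item | 6.2 | Section 8 | SAP 13.2 |
|---|---|---|---|
| 1 Metal implant | yes | – | – |
| 2 Implanted devices | yes | – | – |
| 3 Intracranial intervention or stroke | yes | – | – |
| 4 Major pre-existing disease | yes | – | – |
| 5 Other condition affecting outcome | yes | – | – |
| 6 Writing-hand injury | yes | – | – |
| 7 Intoxication | yes (last item) | – | – |
| 8 Drug or alcohol dependency | no | no | no |
| 9 Chronic treatment, six drug classes | no | three of six | all six, without the limit to chronic use |
| 10 Penetrating brain injury | no | no | no |
| 11 Pregnancy or lactation | no | no | yes |
| 12 Child-bearing potential without contraception | no | no | yes, by implication |

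**Counts**
- Missing from 6.2: 12 − 7 = 5 items. They are the consecutive tail of the list (items 8 to 12), which looks more like an incomplete copy than a decision.
- Of those five, the SAP repeats three (items 9, 11 and 12). The other two (items 8 and 10) stand in the synopsis only.
- Of the six drug classes in item 9, section 8 covers three: MAO inhibitors, antipsychotics and nootropics. The remaining 6 − 3 = 3 (steroids, calcium-channel blockers and anticoagulants) are not restricted anywhere in the protocol outside the synopsis.

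**Two cases that show the conflict**
- A pregnant woman who is otherwise eligible meets no exclusion written in 6.2. The synopsis and SAP 13.2 both exclude her. The screening procedures listed in protocol section 11.1 do not name a pregnancy test.
- Section 6.2 admits patients with well controlled hypertension and no secondary organ damage. If such a patient takes a calcium-channel blocker long term, 6.2 and section 8 raise no objection, while the synopsis and the SAP exclude the patient.

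**Route to the analysis set**
1. Protocol section 13.13.1 has the blind review grade violations as severe, major, minor or none.
2. Under 13.13.3 a severe violation of entry criteria removes the patient from ITT.
3. A patient who falls only under items 8 to 12 violates nothing if 6.2 is the standard. If the synopsis is the standard, the same patient has a violation that may be graded severe.
4. The per-protocol set requires ITT eligibility and no major deviation, so it carries the same ambiguity. Sections 13.10 and 13.13.4 give it the same scientific weight as ITT.

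**Scale per patient:** 1/30 = 3.3% of an arm at the planned 30 per arm. This is only a unit of scale, because the documents give no basis for estimating how many such patients would be enrolled.

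**The case against.** The synopsis is part of the same protocol, so the 12 items are written down. Section 6.2 is silent on five of them; it does not admit those patients. Nothing in the documents makes 6.2 the governing list, and an investigator who reads the whole protocol would see the full set. This stands. It means that such patients could be enrolled, not that they will be.

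Other text catches some of them. Section 8 disallows three drug classes. Within 6.2 itself, the items on psychiatric disorder and on conditions that might influence outcome could exclude a patient with alcohol dependency. The implant and intracranial-intervention items could exclude some penetrating injuries, and the heart-disease wording would exclude many patients on anticoagulants. This also stands, so it would be too strong to say that all five groups pass every criterion in 6.1 and 6.2. The gap is clearest for pregnancy and lactation and for contraception, and next for the three drug classes outside section 8 where the underlying disease is not itself excluded.

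A reader might infer that the synopsis and the SAP both exclude all five groups. They do not: the SAP says nothing on penetrating injury or dependency.

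A reader might also infer that removing such patients after randomisation would bias the comparison. The documents do not support that step. Sections 13.13.1 and 13.16 place the grading in a blind review before decoding, and only severe violations lead to removal from ITT. No mechanism is shown by which one arm would lose more patients than another.

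**Conclusion.** The contradiction is real and should be corrected before it is relied on. Five of the synopsis's 12 exclusions are missing from 6.2, three of those five reappear in the SAP, and neither document ranks the lists. The most serious consequence is that a site reading 6.2 alone could randomise a pregnant or lactating woman whom the synopsis and the SAP exclude. The statistical consequence is narrower: membership of the ITT and per-protocol sets is not uniquely defined for patients caught only by items 8 to 12. That is an ambiguity in the analysis population; bias between arms is not shown.

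The size in patients is unknown. The analysis is affected only if such a patient is enrolled and the violation is then graded severe (for ITT) or at least major (for per protocol).

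It would be tempting to conclude that the synopsis list is the correct one. The documents do not establish that. They show only that four places disagree, including on whether the medication exclusion is limited to chronic use. The point also assumes that section 6.2 of the signed protocol ends where this text does, which the sponsor can check quickly.

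**What to change.** The sponsor should reconcile the synopsis, protocol section 6.2, protocol section 8 and SAP section 13.2 into one confirmed eligibility list. For each of items 8 to 12 it should state whether the exclusion applies. For medication it should settle which drug classes are covered, whether the exclusion is limited to chronic use, and how the entry criterion relates to the concomitant-medication rule in section 8. Copying the synopsis into 6.2 would not be enough, because section 8 and the SAP's broader medication wording would still differ.

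Protocol section 6.4 should then refer to that list for randomisation. Protocol section 13.13.3 and SAP section 10 should name it as the standard against which entry-criteria violations are judged at blind review.

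Cost: wording changes to both documents, with the protocol change going through the ethics committee as an amendment under section 16.4. No additional patients or procedures are needed.
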